2.1 Alzheimer's Disease Data

2.1.1 Study NTRP101-202

NTRP 101-202 was a randomized, double-blind, placebo-controlled, phase 2 trial assessing the safety and tolerability (primary objective) and efficacy (secondary objective) of bryostatin in the treatment of moderately severe to severe Alzheimer's disease subjects. Exploratory objectives characterize the pharmacokinetics (PK) and pharmacodynamics of bryostatin in this subject population. Seven doses of study drug were administered by a 45-minute continuous intravenous (IV) infusion over 12 weeks.

2.1.2 Methodology

Eligible subjects with moderately severe to severe AD were stratified based on Mini Mental State Exam (MMSE-2) scores 4-9 vs. 10-15 and randomized 1:1:1 to one of three treatment arms: 20 μ g, 40 μ g, or placebo for twelve weeks. Trial drug was administered IV by continuous infusion. The first two doses (24 μ g, 48 μ g) of each of the two active treatment arms were a loading dose, 20% higher than the assigned dose (20 μ g, 40 μ g), and were administered one week apart. Thereafter, the assigned dose commenced with the third dose and was administered every other week. Subjects were scheduled to receive seven doses over 12 weeks, with the primary efficacy measure being at Week 13, and a follow-up visit scheduled 30 days from the last dose of trial drug administration.

2.1.3 Demographics

A total of 264 subjects were screened in the trial. Of these, 147 subjects were randomized on a 1:1:1 basis to a treatment group. There were 50 subjects randomized to the placebo treatment group, 49 randomized to the 20 μ g bryostatin treatment group, and 48 randomized to the 40 μ g bryostatin treatment group. A total of 141 of the randomized subjects were treated with investigational product (IP) and were included in the Safety Analysis Set (SAS). A total of 135

subjects provided a post-baseline efficacy assessment and were analyzed as the Full Analysis Set (FAS). A total of 113 subjects out of 147 randomized (76.9%) performed a Week 13 evaluation of the SIB and were analyzed as the Completer Analysis Set (CAS). A total of 106 subjects in the SAS completed the trial (75.2%). A total of 35 subjects in the SAS and 29 subjects in the FAS withdrew early from the trial. The most common reason for early withdrawal was withdrawal of consent (18 subjects), followed by AE (11 subjects).

2.1.4 Safety

Overall, the 20 μ g bryostatin treatment group showed minimal differences from the placebo treatment group in safety assessments. The 40 μ g bryostatin treatment group had significantly greater AEs than the other treatment groups. There was also no clear difference in Serious Adverse events (SAEs) between the 20 μ g bryostatin group and placebo treatment groups, and again the 40 μ g bryostatin treatment group had significantly greater SAEs than the other treatment group. Similarly, the placebo and 20 μ g group had similar numbers of TEAEs (28 events vs 30 events, respectively). The TEAEs observed more often in the 20 μ g treatment group vs placebo were infusion site reaction (8 events vs 3 events in placebo) and diarrhea (5 events vs 1 event in placebo). The 40 μ g treatment group was associated with more TEAEs than either the 20 μ g or placebo treatment groups across multiple system organ classes (SOC).

The most common treatment related TEAEs were grouped infusion reactions, diarrhea, headache, fatigue, and myalgia. Myalgia was seen in 5 subjects; 4 of those subjects were given the higher dose of bryostatin. Myalgia observed was mostly mild and managed with analgesics. There were also more treatment related TEAEs of diarrhea, headache, and fatigue in the higher dose bryostatin group. Both bryostatin treatment groups reported higher rates of infusion site TEAEs, and in particular the 40 μ g bryostatin treatment group reported 4 events of infusion site cellulitis. Although IV infusion-related reactions were also reported more often in the higher dose bryostatin group, none were reported following WebEx-based training on IV infusion and universal precautions, suggesting that this AE can be prevented. The higher dose bryostatin group also reported more TEAEs of seizure and fall compared to the lower dose bryostatin and placebo groups.

A total of 97 (68.8%) subjects in all treatment groups reported 287 separate TEAEs. Of these, 49 (34.8%) subjects reported 107 separate treatment-related TEAEs. There were 8 (16.7%) subjects with 20 treatment-related TEAEs in the placebo treatment group, 17 (37.0%) subjects with 30 events in the 20 μ g bryostatin treatment group, and 24 (51.1%) subjects with 57 events in the 40 μ g bryostatin treatment group. Six subjects had a TEAE that lead to trial drug discontinuation, 2 in the placebo treatment group, 1 in the 20 μ g bryostatin treatment group, and 3 in the 40 μ g bryostatin treatment group. Overall, 43 (30.5%) subjects had a TEAE that was mild in intensity, 46 (32.6%) subjects had a TEAE that was moderate in intensity, and 8 (5.7%) subjects had a TEAE that was severe in intensity.

There was 1 death in the trial, a subject in the 40 μ g bryostatin treatment group who suffered a severe TEAE of worsening of AD that was unrelated to the IP.

There were 12 (8.5%) subjects who had 14 treatment emergent non-fatal SAEs during the trial; 4 subjects with 4 events in the placebo treatment group, 2 subjects with 2 events in the 20 μ g bryostatin treatment group, and 6 subjects with 8 SAEs in the 40 μ g bryostatin treatment group. A total of 4 subjects in the 40 μ g bryostatin treatment group had 4 events that were judged as possibly or probably related to the IP: 3 events of cellulitis, and 1 event of seizure.

There were no apparent differences between treatment groups in laboratory assessments over time. No differences were apparent between treatment groups when examining most vital signs, PEs, and ECG. However, there was a decline in weight in the bryostatin groups, which was more prominent in the higher dose group: 20µg bryostatin treatment group (mean loss of -1.65 ± 2.77 kg) and the 40µg bryostatin treatment group (-2.98 ± 2.10 kg), while there was a slight weight gain in the placebo treatment group (0.442 ± 2.52 kg). Further, 5 subjects in the 40µg bryostatin treatment group had 5 TEAEs of weight decreased, 3 of which were judged to be related to the IP. No weight related TEAEs were observed in the 20µg bryostatin dose group.

There were no differences between treatment groups on the C-SSRS as most subjects did not have suicidal thoughts during the trial, and there were no attempts at suicide by any subject during the trial.

2.1.5 Efficacy

Consistent with the initial hypothesis for bryostatin effects on PKC ϵ and cognition, treatment with 20µg of bryostatin is effective in the treatment of Alzheimer's disease in a FAS and CAS. The overall weight of data shows that subjects treated with 20µg bryostatin displayed significant improvement on the SIB, ADCS-ADL-Sev, and other secondary and exploratory endpoints (one-sided at $\alpha=0.10$), as outlined below.

Baseline scores on the SIB for the FAS were similar across all treatment groups. In the FAS, the treatment difference between the placebo treatment group and the 20µg bryostatin treatment group was statistically significant only at Week 5 (treatment difference $3.0[0.6, 5.3]_{80\%CI}$ $P=0.056$). There were no statistically significant differences between the placebo treatment group and either the 20µg bryostatin treatment group or 40µg bryostatin treatment group at Week 9 or Week 13. Combining the bryostatin treatment groups and comparing with the placebo treatment group also did not produce a statistically significant difference at any time point.

For the CAS, pre-specified along with FAS to assess primary and secondary endpoints, mean scores on the SIB followed the same pattern seen in the FAS. Baseline scores were similar across all treatment groups. There was a statistically significant difference, however, between the placebo treatment group and the 20µg bryostatin treatment group at Week 5 ($P=0.016$), and the treatment difference at Week 13 was also statistically significant ($P=0.070$). Further, when both bryostatin treatment groups were pooled, there was a statistically significant difference between the placebo treatment group and pooled group at Week 5 ($P=0.039$) and a statistically significant treatment difference at Week 13 ($P=0.094$). There were no statistically significant differences between the placebo treatment group and the 40µg bryostatin treatment group at any time point.

In the CAS there were significant differences in the ADCS-ADL-Sev at Week 13 between the placebo treatment group and the 20µg bryostatin treatment group ($P=0.082$), and between the placebo treatment group and pooled bryostatin treatment group ($P=0.087$). There were no statistically significant differences between treatment groups for the ADCS-ADL-Sev, MMSE-2, NPI, or CGI-I assays for any time point in the FAS.

In multiple exploratory analyses adjusting for covariates for the primary endpoint, there were additional significant differences between the placebo treatment group and bryostatin treatment groups. In an MMRM analysis of change from baseline in SIB total score, excluding all subjects from sites that recruited 2 or fewer subjects during the trial, there was a significant difference between the placebo treatment group and the 20µg bryostatin treatment group at Week 5 ($P=0.068$). There was a significant difference between the placebo treatment group and the 20µg

bryostatin treatment group ($P=0.031$), and between the placebo treatment group and the pooled bryostatin treatment group in an MMRM analysis of change from baseline in SIB total score at the 30-day follow up visit ($P=0.041$). When an ANCOVA was performed to assess site effect on SIB, there was a significant difference between the placebo treatment group and 20 μ g bryostatin treatment group ($P=0.032$), and between the placebo treatment group and pooled bryostatin treatment groups ($P=0.049$) at Week 5. In an ANCOVA of change from baseline in SIB total score, with use of AChEI or memantine at baseline as an additional covariate, at Week 5 the 20 μ g bryostatin treatment group and pooled bryostatin treatment groups had statistically significant treatment differences from the placebo treatment group ($P=0.024$ and $P=0.027$, respectively). In multiple exploratory analyses adjusting for covariates for secondary endpoints, there were statistically significant differences between the placebo treatment group and the 20 μ g bryostatin treatment group at Week 5 ($P=0.062$), and the placebo treatment group and pooled bryostatin treatment group at Week 5 ($P=0.041$) when performing an ANCOVA of change from baseline in ADCS-ADL-Sev total score for subjects with > median baseline ADCS-ADL-Sev total score. There was a statistically significant difference between the placebo and 40 μ g bryostatin treatment groups at Week 5 ($P=0.099$) in an ANCOVA of change from baseline in NPI Total score to assess site affects. When performing an ANCOVA of change from baseline in NPI total score for subjects with > median baseline NPI total score, there were statistically significant differences between the placebo treatment group and the 40 μ g bryostatin treatment group at Week 9 ($P=0.054$) and Week 13 ($P=0.096$).

No clear differences were apparent between treatment groups for Caregiver distress on the NPI, each NPI subscore at baseline, or on the NPI 10-item score.

The results for SIB score from the MSSE-2 Stratum 1 analysis show the 20 μ g bryostatin treatment group had a more positive response than any treatment group at Week 5 and Week 9 and the 40 μ g bryostatin treatment group had a slightly better response at Week 13. Results for SIB score in the MSSE-2 Stratum 2 analysis show the positive response varied across time point and treatment group. The placebo treatment group showed greater improvement in ADCS-ADL-Sev total score at Weeks 5 and 9 than either bryostatin treatment group in Stratum 1 or 2, and also at Week 13 in Stratum 2. At Week 13 in Stratum 1, the 20 μ g bryostatin treatment group showed the best response compared to placebo or the 40 μ g bryostatin treatment group.

There was a significant difference in the FAS between the placebo treatment group and the 20 μ g bryostatin treatment group ($P=0.031$), and between the placebo treatment group and the pooled bryostatin treatment group ($P=0.041$) in an MMRM analysis of change from baseline in SIB total score at the 30-day follow up visit.

Additional post-hoc analyses were performed on the TEAE by MMSE-2 baseline strata, SIB by BSA-adjusted Dose, ADCS-ADL-Sev by BSA-adjusted Dose, TEAE by BSA-adjusted Dose, SIB by memantine use, ADCS-ADL-Sev by memantine use, the NPI 10-item total score by memantine use, and administration site-specific TEAE. The SIB and ADCS-ADL-Sev scores also appeared to be affected by BSA-adjusted dose, as the lowest tertile of bryostatin dose in general had a better response to treatment than higher tertiles or placebo (these data were also not analyzed statistically). Subjects treated with bryostatin who did not take memantine at baseline had significantly better improvement in SIB score compared to the placebo group in an MMRM analyses of SIB total score in both the CAS and FAS. Both the pooled bryostatin and 20 μ g bryostatin treatment groups had significantly better scores than the placebo treatment group at Weeks 5, 13, and at 30-day Follow-up. Similar results (which were not statistically analyzed) were seen in the ADCS-ADL-Sev test and in the NPI 10-item score.

2.1.6 Pharmacokinetics

Mean plasma bryostatin concentrations increased approximately proportional to dose for an increase in dose between 20 µg and 40 µg, infused IV over 45 minutes. The median T_{max} occurred at the end of the 45-min infusion.

Mean C_{max} ranged from 0.563 ng/mL to 0.653 ng/mL after 20 µg and from 0.792 ng/mL to 1.34 ng/mL after 40 µg. Mean T_{1/2} ranged from 1.33 h to 5.37 h. Mean CL was similar for both dose levels and ranged from 24.97 L/h to 28.42 L/h for Weeks 0 and 3. The mean CL on Weeks 7 and 11 was slightly lower, ranging from 13.38 L/h to 23.91 L/h.

Within a given dose level, the ranges of values for C_{max}, AUC_{last}, and AUC_{inf} were consistent across weeks and there was no indication of systemic accumulation of bryostatin during administration of bryostatin once every 2 weeks.

2.1.7 Summary

Bryostatin treatment was in general safe to use and well tolerated.

The 20µg bryostatin treatment group had similar numbers of TEAEs to the placebo treatment group except in injection site reactions and diarrhea. The 40µg treatment group had more TEAEs and SAEs than the 20µg or placebo treatment groups across many SOCs.

The 40µg dose of bryostatin was associated with more TEAEs. With a decrease in systemic CL especially noted with 40µg bryostatin dosing, the higher drug exposure may further explain the increased number of TEAEs. The most common treatment related TEAEs were diarrhea, headache, fatigue, and myalgia, and all were reported in greater frequency with the 40µg dose of bryostatin. Subjects given the 40µg dose of bryostatin also reported more TEAEs of seizure and fall.

The primary efficacy endpoint for the SIB and secondary efficacy endpoint for the ADCS-ADL-Sev was met in the CAS with the 20µg dose, which was statistically significantly different from placebo at Weeks 5 and 13. The 40µg dose was not statistically significant from the placebo. SIB improvement was significant for the Week 5 FAS measurement ($p < .056$). No other primary or secondary endpoints were met in the FAS.

Multiple exploratory analyses in the FAS for covariates in the primary and secondary endpoints revealed additional significant differences, but these occurred predominantly at the Week 5 time point.

2.2 Study NTRP101-201

This was a randomized, double-blind, Placebo-controlled safety study of a single dose of bryostatin in subjects with mild to moderate AD (MMSE: 14-26). Subjects were randomized 2:1 to receive bryostatin 25µg/m² or Placebo. The primary objective was to evaluate the safety and tolerability of bryostatin by the incidence of AEs and SAEs. Secondary safety endpoints included assessment of physical examination, hematology including complete blood count (CBC) and platelet count, coagulation parameters, serum chemistries, ECG, urinalysis and vital signs.

The primary efficacy endpoint was a composite end point of change from baseline in the Hopkins Verbal Learning Test-Revised (HVLTR) delayed recall and Repeatable Battery of Assessments for Neuropsychological Status (RBANS) figure recall at 48 hours post study drug infusion.

The study included single dose PK, and measurement of PKCε in peripheral blood mononuclear cells (PBMCs) as a potential biomarker.

2.2.1 Results

2.2.1.1 Demographics

The study enrolled nine subjects, 4 male and 5 female, with a mean age of 71.8 ± 7.4 years (range 62 to 82). The mean MMSE-2 at baseline was 22.5 for the three placebo subjects (range 19-24) and 22 (range 16-26) for the six bryostatin treated subjects.

2.2.1.2 Safety

Bryostatin was well tolerated. There were no deaths or SAEs reported. No subjects had an AE leading to withdrawal during the study. There were five treatment emergent adverse events occurring in three subjects: headache, dizziness, and papular rash. There were no reported episodes of myalgia, a known side effect of bryostatin. The only adverse event in the bryostatin treated group was headache, which was not considered related to study drug. All adverse events were mild and resolved without treatment. All laboratory assessments, including hematology, chemistry, coagulation, renal function and liver function as well as cardiac assessments were unremarkable after treatment and there was no clinically significant change in any vital signs.

2.2.1.3 Efficacy

There was no difference in HVLt-R delayed recall or the RBANS delayed figure recall at 48 hours. Additional time points of assessment for these measures (day 2, day 4 and day 15) did not indicate any difference between groups. Additional endpoints included the change from baseline in Digit Symbol Coding (DSC), and MMSE-2 at various time points. There was no difference in mean values between groups for these endpoints at any time point. Both the treatment and the Placebo group showed an improvement in the MMSE-2 score most likely due to practice effects since the MMSE-2 was administered five times in 2 weeks.

In summary, there was no clinically significant difference between the mean or mean change from baseline between bryostatin and placebo in the HVLt-R or MMSE-2 assessments or any other efficacy assessments to suggest a treatment effect after a single dose of $255 \mu\text{g}/\text{m}^2$ bryostatin.

2.2.1.4 Pharmacokinetics

The pharmacokinetics of bryostatin were assessed in 6 subjects following $25 \mu\text{g}/\text{m}^2$ bryostatin administered as a single 1-hour IV infusion. Individual bryostatin plasma concentrations were observed to increase and approach steady-state within the 1 hour infusion periods, and then rapidly decrease following the end of the infusion. The bryostatin maximum plasma concentrations occurred at the end of the IV infusions, and had a mean (\pm standard deviation (SD)) value of 1.09 ± 0.25 ng/mL. A terminal elimination rate could not be calculated for most subjects due to sampling frequency, the rapid drug elimination, and the sensitivity limitations of the assay. Based on the observed individual bryostatin plasma concentration profiles, the elimination $t_{1/2}$ associated with the observed drug exposure was estimated to be less than 30 minutes. Total drug CL was

observed to be high (~ 40 L/h), consistent across the individual administered doses, and did not appear to be related to body weight, BSA, or sex. The bryostatin pharmacokinetic parameters were observed to have low to moderate intersubject variability.

2.2.1.5 Pharmacodynamics/ PKCε

Preliminary assessment of PKCε concentration in PBMCs suggests there is an increase in the total amount of PKCε (cytosol plus membrane bound concentration) following treatment with bryostatin. Additional analysis is underway to further characterize the increase and pharmacodynamics.

2.2.1.6 Conclusions

This was the first double-blind assessment of the safety of bryostatin treatment in subjects with Alzheimer's disease. The study met its primary endpoint of safety and tolerability. Bryostatin appears safe and well tolerated in this cohort of subjects with mild to moderate Alzheimer's disease. No improvement was detected in cognitive function on the efficacy measurements though the study was not powered to detect cognitive benefit. There was no evidence of an adverse effect on cognition following treatment with bryostatin.

3 STUDY OBJECTIVES AND HYPOTHESIS

3.0 Primary Objective

To evaluate the safety, tolerability and efficacy of bryostatin for the treatment of moderately severe to severe Alzheimer's disease in subjects not receiving concurrent memantine treatment.

3.1 Hypothesis

Patients treated with bryostatin will experience a greater improvement in cognitive function as measured by the SIB from baseline to the primary efficacy endpoint after 12 weeks of treatment, as compared to patients on placebo during the same time period. The null hypothesis will be rejected at a significance level of a two-sided $\alpha = 0.05$. The test of the null hypothesis will be a superiority test based on the two-sample t-test, and only an improvement in the SIB score from baseline is of clinical significance.

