9 DATA ANALYSIS / STATISTICAL METHODS

Detailed methodology for summary and statistical analyses of the data collected in this study will be documented in a Statistical Analysis Plan (SAP). This separate document will be finalized prior to study unblinding and conduct of any statistical analyses. The SAP may modify and will take precedence over the plans outlined in the protocol; however, any major modifications or modification of the primary endpoint definition and/or its analysis will also be reflected in a protocol amendment.

Descriptive summaries of safety and efficacy data including number of evaluable subjects, mean, median, SD, maximum and minimum for continuous variables will be provided by treatment group and scheduled visit. Categorical variables will be presented showing number evaluable, frequencies and percentages. In addition, the same descriptive statistics will be provided for changes from baseline at each post-baseline visit.

The primary efficacy analyses of the primary endpoint will be conducted on data collected through Week 13.

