9.4 Analysis of Primary Efficacy Endpoint

The primary endpoint for this study is the change from baseline to Week 13 in the SIB total score. The primary analysis will be conducted on FAS population. The CAS population will be used as a supportive analysis. All statistical tests for efficacy will be two-sided tests, with $\alpha=0.05$.

Based on the review of patients not treated with memantine in the NTRP 101-202 clinical trial, the expected number of patients who will drop out of the study prematurely will not be significant. For efficacy evaluations, multiple imputation methods will be used to handle missing data. This imputation method is a robust method to impute missing measurements. The imputation will be carried out in SAS version 9.4 or later using PROC MI. Each imputation model will include the stratification factor (i.e., MMSE-2 score (4-9 vs. 10-15)) as a covariate in the model..

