9.5 Secondary Efficacy Endpoints

9.5.1 Changes from baseline at Weeks 5, 9 and 15 in the SIB total score

The change from baseline at Week 5, 9 and 15 in the SIB total score will be summarized descriptively and compared using ANCOVA adjusted for baseline SIB total score. If the normality assumption is not met, a non-parametric method or a rank-ANCOVA analysis will be used.

9.5.2 The changes from baseline at Weeks 5, 9, 13 and 15 in the SIB total score for subjects in the MMSE-2 4-9 stratification group

Similar analysis methods as the primary endpoint will be used for analysis of this endpoint.

9.5.3 The changes from baseline at Weeks 5, 9, 13 and 15 in the SIB total score for subjects in the MMSE-2 10-15 stratification group

Similar analysis methods as the primary endpoint will be used for analysis of this endpoint.

9.5.4 Individual patient's slope over time in SIB total score evaluated via Weeks 0, 5, 9 and 13

Individual-specific SIB slopes will be estimated for all patients over each person's available SIB outcome measures. An indicator will be assigned to each patient depending on the sign of the SIB slope β (i.e. $I=-1$ if $\beta < 0$; 1 if $\beta > 0$; no value otherwise). The proportions of patients with $I=1$ and, respectively, -1 will be compared using logistic regression to assess the overall trend between treatments. In addition, an overall population averaged slope will be estimated for each treatment arm, and two-sample t-test will be used to assess the difference between treatments.

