8.2.1 Primary Efficacy Endpoint

The primary endpoint for this study is the change from baseline to Week 13 in the SIB total score.

The change from baseline to Week 13 in the SIB total score will be summarized descriptively and compared using Analysis of Covariance (ANCOVA) adjusted for baseline SIB total score.

If the normality assumption is not met, a non-parametric method or a rank-ANCOVA analysis (i.e., an ANCOVA analysis on rank-transformed data) will be used.

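### Protocol 3.1 names a two-sample t-test for the primary hypothesis and SAP 8.2.1 names baseline-adjusted ANCOVA; the SAP most likely governs, but the amendment that Protocol 9 requires for such a change was not made.

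*Protocol*

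**What the plan says.** - **Protocol 3.1 (Hypothesis):** "The test of the null hypothesis will be a superiority test based on the two-sample t-test", at two-sided 0.05. The same sentence adds that "only an improvement in the SIB score from baseline is of clinical significance".
- **Protocol 9.0 (Sample Size):** power is computed for the two-sample t-test on Week 13 change.
- **Protocol 9.4 (Primary Efficacy Endpoint):** "The primary endpoint for this study is the change from baseline to Week 13 in the SIB total score". The section goes on to give the population (FAS, with CAS as support), the alpha and the imputation approach, but no test.
- **Protocol 9.5.1:** SIB change at Weeks 5, 9 and 15, all secondary endpoints, is "compared using ANCOVA adjusted for baseline SIB total score". Sections 9.5.2, 9.5.3 and 9.6 then borrow the method of the primary endpoint, which 9.4 has not stated.
- **SAP 8.2.1:** the Week 13 primary endpoint is "compared using Analysis of Covariance (ANCOVA) adjusted for baseline SIB total score". The fallback reads "If the normality assumption is not met, a non-parametric method or a rank-ANCOVA analysis".
- **SAP 7.6:** the stratification factor and baseline variables such as age, sex or severity are optional covariates.
- **Protocol 9 (opening text):** "The SAP may modify and will take precedence over the plans outlined in the protocol". The same sentence adds the condition that "modification of the primary endpoint definition and/or its analysis will also be reflected in a protocol amendment".
- **SAP 1:** the SAP was prepared from protocol Version 3.0 of 18 April 2019.

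**The concern.** The title calls this trial confirmatory, and one p-value decides its primary result. Within the protocol, the t-test is the only test attached to the primary hypothesis. Within the SAP it is ANCOVA. On the same data these can fall on opposite sides of 0.05.

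The protocol has a rule for resolving such a conflict, but the rule comes with a condition that the current text does not meet. Version 3.0 revised the definition of the primary endpoint and left the t-test in 3.1. The Version 3.0 entry in Appendix 3 lists no change of test. If the two results differed, a critic could cite the protocol against the SAP, and a correction made after unblinding could look driven by the result.

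**Working it through.** **Inputs from the documents.** SD of Week 13 change 6.8 (20 µg) and 6.7 (placebo); 50 per arm, or 37 per arm after 25% dropout; effects of 4.0 to 5.5 points; observed post hoc difference 5.4 points; two-sided alpha 0.05 (Protocol 9.0, SAP 3). Pooled SD = √[(6.8² + 6.7²)/2] = 6.75.

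**Input not in the documents.** The correlation between baseline SIB and change. I take its absolute value r from 0 to 0.5 as an assumption.

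**Step 1: reproduce the plan's power (t-test).** Noncentrality = d / [SD·√(2/n)], df = 2n − 2.
- n = 50, d = 4.0: 4 / (6.75 × 0.2) = 4 / 1.35 = 2.96, power 83.5% (plan: 83%).
- n = 37, d = 4.5: 4.5 / (6.75 × 0.2325) = 4.5 / 1.569 = 2.87, power 80.8% (plan: 80%).
- All cells: 83.5 / 91.0 / 95.6 / 98.1% at 50 per arm (plan 83 / 91 / 95 / 98) and 80.8 / 88.2 / 93.3% at 37 per arm (plan 80 / 88 / 93). The tables reproduce.

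**Step 2: power if ANCOVA is the test.** Replace SD by SD·√(1 − r²), with df = 2n − 3. Example: n = 50, d = 4, r = 0.3 gives 6.75 × 0.954 = 6.44, noncentrality 4 / (6.44 × 0.2) = 3.11, power 86.8%.

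| Setting | r = 0 | 0.2 | 0.3 | 0.5 |
|---|---|---|---|---|
| n = 50, 4.0 points | 83.5% | 84.9% | 86.8% | 92.3% |
| n = 37, 4.5 points | 80.7% | 82.3% | 84.3% | 90.4% |

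This formula ignores chance baseline imbalance. In simulation at r = 0, n = 37 and 4.5 points, ANCOVA reached 79.7% and the t-test 80.4%, so at zero correlation ANCOVA gives up a fraction of a point.

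**Step 3: how often the verdicts differ at 0.05.** Both tests were run on the same simulated data: 20,000 trials per setting, SD 6.75, complete normal data.

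| n per arm | Effect | r = 0 | 0.2 | 0.3 | 0.5 |
|---|---|---|---|---|---|
| 50 | 4.0 | 1.7% | 3.8% | 6.2% | 11.0% |
| 50 | 5.4 | 0.5% | 0.8% | 1.4% | 2.0% |
| 37 | 4.0 | 2.7% | 5.5% | 8.7% | 15.6% |
| 37 | 4.5 | 2.3% | 4.4% | 7.2% | 12.1% |
| 37 | 5.4 | 1.3% | 2.4% | 3.3% | 5.7% |

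Repeat runs moved these by a few tenths of a point; for 50 per arm and 5.4 points, one gave 0.4 to 2.2%. Disagreement runs both ways. At n = 50, 4 points and r = 0.3, ANCOVA alone is significant in 4.6% of trials and the t-test alone in 1.6%.

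**Step 4: no true effect.** Each test alone rejects in about 5% of trials. At least one rejects in 5.5 / 5.8 / 6.2 / 7.0% (n = 50) and 5.3 / 6.0 / 6.8 / 7.2% (n = 37) for r = 0 / 0.2 / 0.3 / 0.5. Those rates apply only if success is claimed on whichever test is significant.

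**The case against.** The best defence is that the documents rank the two tests. Protocol 9 puts the SAP above the protocol and requires it to be final before unblinding. ANCOVA is already in the protocol for SIB at the other visits, and the t-test in 3.1 matches the power basis. On this view all that is missing is a conforming edit to 3.1. Most of this stands, and it is why the point is not graded higher. It does not close the matter, because the precedence sentence carries its own amendment condition. Nor did the SAP merely fill the gap in 9.4, since 3.1 had already named a test.

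A reader might infer three stronger things that the documents do not support:

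- **That the tests have equal standing and either may be claimed.** The precedence clause says otherwise.
- **That type I error is inflated.** Nothing in either document permits choosing the test after unblinding, and each test alone holds 5%.
- **That the clinical-significance clause in 3.1 adds a within-arm success criterion, which a drug that only prevents decline would fail.** The section opens by setting the bryostatin gain against placebo over the same period, and the test it names is two-sample. SAP 5 states a between-arm hypothesis, and no within-arm test is planned. The clause is naturally read as naming the favourable direction after a two-sided alpha. It needs clearer wording and no more.

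The size also depends on the effect: at the 5.4 points that guided the sample size, the tests seldom disagree.

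**Conclusion.** The inconsistency is real and should be fixed. Two different tests are on record for the primary hypothesis. The SAP's ANCOVA most likely governs, and the protocol's own condition for that change is unmet in Version 3.0.

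The tests would disagree in about 2-11% of trials at 4 points with 50 per arm and about 3-16% with 37 per arm. At 5.4 points this falls to about 0.4-2% and 1-6%. A type I error rate of about 5.3-7.2% would arise only from choosing the test after unblinding.

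These figures rest on SD 6.75, complete normal data and an assumed absolute correlation of 0 to 0.5. They include neither multiple imputation nor an MMSE-2 stratum effect, so the 37-per-arm rows describe complete cases rather than the planned FAS analysis. This is a conflict of specification and not a power error.

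Pointing to the SAP's ANCOVA would not by itself leave one primary test. The unspecified non-parametric alternative in SAP 8.2.1 and the optional covariates in SAP 7.6 lie inside the governing document, where precedence cannot settle them.

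**What to change.** Before unblinding:

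1. Amend Protocol 3.1 and 9.4 to name ANCOVA adjusted for baseline SIB, on the FAS with multiple imputation, as the single primary test. Label the t-test as the basis of the power calculation or as a sensitivity analysis.
2. In SAP 7.6 and 8.2.1, fix the primary model's covariates as baseline SIB and the MMSE-2 stratum, in place of the optional list.
3. In SAP 8.2.1, make rank-ANCOVA a prespecified sensitivity analysis, so that a normality check cannot replace the primary test.
4. As a minor clarification, reword the clinical-significance clause in Protocol 3.1 to say that it means a between-arm difference favouring bryostatin.

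The cost is a short protocol amendment and matching edits to two SAP sections. No procedure, visit or sample size changes. The power tables can stay, because ANCOVA power is essentially equal to or higher than t-test power.
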